9.4. Deaths, Serious Adverse Events and other Significant Adverse Events

Serious Adverse Events were documented from the time of the first study vaccination (Day 1 (Visit 01)) through the end of the study.

A listing of death and other serious adverse events will be presented by Subject ID, Age (years) Adverse Event Description, Adverse Event Onset Date/End Date, Last Dose Received/Days Post Dose, Reason Reported as an SAE, Relationship to Treatment, Alternate Etiology if not Related, Outcome, and Duration of Event (days) (Table 58).

9.5. Pregnancies

For any subjects in the Safety population who became pregnant during the study, every attempt will be made to follow these subjects to completion of pregnancy to document the outcome, including information regarding any complications with pregnancy and/or delivery. Pregnancies and outcomes will be presented in Listing 27, Listing 28, Listing 29, Listing 30, and Listing 31.

9.6. Clinical Laboratory Evaluations

Clinical safety laboratory evaluations were performed at baseline and approximately 8 days after Dose 1 and Dose 2 of study vaccination. The grading scale for clinical laboratory evaluations will be presented in Table 12. Subject visits with abnormal laboratory results, Grade 1 severity or higher, will be presented in Table 59 and Table 60 for Chemistry and Hematology parameters, respectively.

The distribution of chemistry results by severity, study day, and vaccination group will be presented in Table 61, Table 62, Table 63, and Table 64. Descriptive statistics including mean, standard deviation, median, minimum, and maximum by study day, will be summarized for each parameter in Table 65, Table 66, and Table 67. Plots illustrating the change from baseline for each chemistry laboratory parameter will be presented in Figure 41.

The distribution of hematology results by severity, study day, and vaccination group will be presented in Table 68, Table 69, Table 70, and Table 71. Descriptive statistics including mean, standard deviation, median, minimum, and maximum by study day, will be summarized for each parameter in Table 72, Table 73, and Table 74. Plots illustrating the change from baseline for each hematology laboratory parameter will be presented in Figure 42.

A complete listing of individual clinical laboratory results will be presented in Listing 22 and Listing 23.

9.7. Vital Signs and Physical Evaluations

Vital sign measurements blood pressure, oral temperature, and pulse. Vital signs were assessed at Day 1, Day 22, and Day 172, and as needed at the other study visits. The grading system for vital signs can be found in Table 11. Vital signs will be tabulated by visit and study arm (Table 75, Table 76, Table 77, Table 78, and Table 79). A listing of vital findings will be presented in Listing 24.

Physical examinations may be conducted at any study visit based on indicated symptoms. A listing of physical exam findings will be presented in Listing 25.

9.8. Concomitant Medications

All current medications and medications taken in the 30 days before Study Day 1 (prescription and over-the-counter drugs) will be recorded in the eCRF, as well as vaccinations, vitamins, and supplements, through 21 days after the second M-001 study injection. All concomitant medications and vaccinations taken within 60 days prior to signing the ICF will be recorded on the appropriate data collection form prior to the first study vaccination. Concomitant medications (vaccines only) will be recorded on the appropriate data collection form after Visit 7 through the end of the study. Assessment of eligibility will also include a review of prohibited medications (per the exclusion criteria).

A by-subject listing of the concomitant medication use will be presented (Listing 26). The use of concomitant medications during the study will be summarized by ATC1, ATC2 code and study arm for the Safety population (Table 80).

10. REPORTING CONVENTIONS

P-values ≥0.001 and ≤0.999 will be reported to 3 decimal places; p-values less than 0.001 will be reported as "<0.001" The mean, standard deviation, and other statistics will be reported to 1 decimal place greater than the original data. The minimum and maximum will use the same number of decimal places as the original data. Proportions will be presented as 2 decimal places; values greater than zero but <0.01 will be presented as "<0.01". Percentages will be reported to the nearest whole number; values greater than zero but < 1% will be presented as "<1"; values greater than 99% but less than 100% will be reported as >99%. Estimated parameters, not on the same scale as raw observations (e.g. regression coefficients) will be reported to 3 significant figures.

11. TECHNICAL DETAILS

SAS version 9.4 or above and R version 3.6 or above will be used to generate all tables, figures and listings.

12. SUMMARY OF CHANGES IN THE CONDUCT OF THE STUDY OR PLANNED ANALYSES

After the data format for the primary analysis was confirmed, the planned analysis was changed from what is described in the protocol. Instead of utilizing a normal approximation, a Poisson regression model will be fit to test for differences between study arms, as described in Section 8.1.

Additionally, the modified Intent-to-Treat population will only be used as a sensitivity analysis for the primary objective. Originally it was also planned for secondary and exploratory objectives involving antibody responses, but these will not be done in the interest of conciseness.

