11.5.3. Humoral Immunogenicity Data

Summaries and analysis of immunogenicity data will be presented for the ITT and PP populations; the PP population will be considered the primary analysis.

Immune responses in terms of strain-specific (IIV4 strains) HAI and Neut antibody titers will be summarized by treatment arm at each time point. Analyses at all time points will include proportion of subjects with titers ≥ 40 and geometric mean titers (GMTs). Additionally the proportion of subjects achieving seroconversion from Day 172 to Day 200 (defined as either a pre-vaccination titer < 10 and a post-vaccination titer ≥ 40 or a pre-vaccination titer ≥ 10 and a minimum four-fold rise in post-vaccination antibody titer) will be presented. All summaries will include the corresponding 95% confidence intervals.

The proportion of subjects with seroconversion from Day 172 to 200 will be compared to evaluate the effect of M-001 priming using a two-sided Likelihood Ratio Test.

M-001 antibody response will be summarized by GMTs the proportion of subjects achieving seroconversion (defined as a minimum four-fold rise in post-vaccination ELISA antibody titer) at each time point, with corresponding 95% confidence intervals.

The correlation between HAI, Neut, and M-001 antibody titers will be evaluated. Plots such as reverse cumulative distributions or longitudinal presentations of GMTs will be presented for each assay.

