6.3.1. Modified Intent-to-Treat (mITT) Population

The modified intent-to-treat (mITT) population includes all subjects who received at least one dose of study vaccine and contributed at least one post-study vaccination venous blood sample for immunogenicity testing for which valid results were reported.

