6.3.2. Per Protocol Population

The per protocol (PP) population includes all subjects in the mITT subset with the following exclusions:

- Data from all available visits for subjects found to be ineligible at baseline
- Data from all visits subsequent to major protocol deviations, such as:
 - Second or third study vaccination not received

- Second or third study vaccination received out of window
- Receipt of non-study licensed live vaccine within 30 days before or 21 days after each study vaccination
- Receipt of non-study licensed inactivated vaccine within 14 days before or 21 days after each study vaccination
- Receipt of non-study seasonal influenza vaccine (live or inactivated) within 30 days before or for the duration of the study
- o Receipt of immunosuppressive therapy (e.g., corticosteroids) within 30 days before or after each of the first two study vaccinations (Dose 1 and Dose 2)
- Data from any visit that occurs out of window
 - O Visit 03: Day 14 + 2 days post vaccination 1
 - O Visit 04: Day 22 + 2 days post vaccination 1
 - Visit 06: Day 14 + 2 days post vaccination 2
 - Visit 07: Day 21 + 7 days post vaccination 2
 - Visit 08: Day 56 + 7 days post vaccination 2
 - O Visit 09: Day 150 ± 30 days post vaccination 2
 - O Visit 10: Day 14 + 3 days post vaccination 3
 - O Visit 11: Day 28 + 7 days post vaccination 3

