8. IMMUNOGENICITY EVALUATION

Analysis of all immune responses will be conducted using the PP population. In addition, for the primary endpoint, analysis conducted with the mITT population will be used as a sensitivity analysis. Percentages of cell subset responses will be measured by flow cytometry as described in Section 4.5.2.

Data listings of HAI and Neut assay results as reported by the central immunogenicity laboratory will be provided in Listing 8, Listing 9, Listing 10, Listing 11, Listing 12, Listing 13, Listing 14, and Listing 15. ELISA assay results will be provided in Listing 16, and flow cytometry results will be provided in Listing 17 and Listing 18.

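### The SAP drops the supporting mITT analysis of the antibody endpoints for brevity, so HAI/Neut responses to IIV4 are summarized in the per-protocol population only and SAP 6.1 refers to an mITT antibody analysis that no longer exists

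*SAP*

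**What the plan says.** Protocol 11.5.3 (Humoral Immunogenicity Data) states: "Summaries and analysis of immunogenicity data will be presented for the ITT and PP populations; the PP population will be considered the primary analysis". Protocol 11.5.1 defines no plain intent-to-treat set, only mITT, so the term in 11.5.3 has to mean mITT. The same section names the comparison of seroconversion from Day 172 to Day 200 as the evaluation of M-001 priming.

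SAP section 8 narrows this: "Analysis of all immune responses will be conducted using the PP population". The mITT set survives in one role: "for the primary endpoint, analysis conducted with the mITT population will be used as a sensitivity analysis". SAP section 12 records the change. It confirms that mITT had been intended for the secondary and exploratory antibody objectives as well, and says of those analyses that "these will not be done in the interest of conciseness".

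The SAP shells agree with sections 8 and 12. HAI/Neut Tables 30 to 37, Figures 10 to 29 and ELISA Table 44 are all per protocol. The only mITT immunogenicity exhibits are T cell Tables 24 and 25 and Figures 3 and 5.

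SAP 6.1 was not brought into line. If enough subjects have intercurrent infections that could affect the vaccine-strain immunoassays, it plans a sensitivity analysis without them, to be compared qualitatively with the mITT and PP analyses.

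**The concern.** The PP set in SAP 6.3.2 removes data after events that follow randomization: a missed or out-of-window second or third dose, a non-study vaccine, immunosuppressive therapy, or a visit outside its window. By Day 200 a subject has had every opportunity to meet one of these, so the antibody response to IIV4 is read in the set that has been filtered longest. A supporting analysis in a wider set shows whether the HAI/Neut estimates depend on that filter. The protocol planned one, and the only reason given for removing it is the length of the report, which is not a statistical reason.

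The second problem is internal. The vaccine-strain assays that SAP 6.1 has in mind are the HAI and neutralization assays. After section 12, no mITT result for them exists to compare with.

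**Working it through.** **1. What an mITT analysis would recover.** The mITT set (SAP 6.3.1) takes any subject who had one dose and "contributed at least one post-study vaccination venous blood sample for immunogenicity testing for which valid results were reported". To count in seroconversion from Day 172 to Day 200, a subject also needs a titer at both visits, because SAP 6.5 imputes nothing. Taking the PP exclusions in turn:

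- "Second or third study vaccination not received": mostly not recovered. Under Protocol 6.3 these subjects continue safety follow-up, possibly by phone, and are asked for one antibody sample about 21 days after their last M-001 dose. No Day 172 or Day 200 serum is scheduled for them there, although Protocol 5.4.4 encourages vaccinated subjects to keep giving blood and the MOP may add follow-up.
- Dose 2 or 3 out of window: should be rare. Protocol 5.4.3 and 6.3 allow no exceptions to the windows, and the Dose 3 window runs from Day 142 to Day 202.
- Visit out of window: recovered. Most windows are one-sided (Visit 11 is +7 days only), so an early sample is lost to PP.
- Non-study vaccine or immunosuppressive therapy: recovered if the samples were drawn.
- Ineligible at baseline: recovered on the SAP 6.3.1 definition. The Table 14 shell, however, lists baseline ineligibility as a reason for exclusion from mITT, so those two places need to agree.

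**2. The plan's own precision figure.** Protocol Table 9 and SAP Table 4 give an exact 95% interval of 36.8% to 63.2% for a 50% response in one arm of 60. Clopper-Pearson limits are the 0.025 quantile of Beta(x, n−x+1) and the 0.975 quantile of Beta(x+1, n−x). With x = 30 and n = 60 they are 36.8% and 63.2%, which reproduces the figure. The half-width is (63.2 − 36.8)/2 = 13.2 points.

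**3. Bounds for one arm.** Assumptions, none of them from the documents: PP seroconversion of about 50%, m of 60 subjects excluded, and every excluded subject with both titers. If x of n = 60 − m PP subjects seroconvert, the full-arm rate lies between x/60 (no excluded subject responds) and (x + m)/60 (all respond).

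| m | PP rate | Full-arm range | Largest shift |
|---|---|---|---|
| 3 | 28/57 = 49.1% | 28/60 = 46.7% to 31/60 = 51.7% | about 2.5 points |
| 6 | 27/54 = 50.0% | 27/60 = 45.0% to 33/60 = 55.0% | 5 points |
| 9 | 26/51 = 51.0% | 26/60 = 43.3% to 35/60 = 58.3% | 7 to 8 points |

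Only m = 3 has a link to the documents: 5% of 60. That 5% (Protocol 11.3.3, SAP section 5) is for the primary outcome, not Day 200, and it includes subjects with no data, whom mITT cannot recover either.

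**4. Bounds for the difference between arms.** Assume PP rates near 60% and 40% and equal exclusions per arm, and use the likelihood ratio test named in Protocol 11.5.3.

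- 3 excluded per arm: PP 34/57 against 23/57, difference 19.3 points, p = 0.039. The least favorable full-arm result is 34/60 − 26/60 = 13.3 points (p = 0.144); the most favorable is 37/60 − 23/60 = 23.3 points.
- 6 excluded per arm: PP 32/54 against 22/54, difference 18.5 points, p = 0.054. The full-arm range is 32/60 − 28/60 = 6.7 to 38/60 − 22/60 = 26.7 points.

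These are all-or-none limits that show what could happen. They are not estimates of what will.

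**The case against.** The strongest reply is that little has been lost. PP was the primary humoral population from the start, so only a supporting display has gone, and section 12 says so openly. These are secondary endpoints of a Phase II trial. SAP 8.2 only summarizes them and no longer includes the protocol's likelihood ratio test, so there is no between-arm test for mITT to support. Table 14 shows exclusions by arm, reason and visit. Listing 5 marks excluded subjects whose results were available, and Listings 8 to 15 give individual titers. A determined reader could rebuild the mITT figures. A worst-case shift of 2.5 points in one arm is about one fifth of the 13.2-point half-width (2.5/13.2 = 0.19).

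Most of this stands, and it limits the weight of the point. It does not remove it: counts of exclusions do not show whether the estimates change, and leaving the reader to rebuild an analysis from listings does not replace presenting it. Nor does it answer the unmatched reference in SAP 6.1.

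A reader might also infer that doses withheld for adverse events after M-001 bias the PP result and that mITT would expose this. The documents do not support that as the main reason. Withholding could differ by arm, but those subjects mostly lack the Day 172 and Day 200 sera and would be missing from both analyses.

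**Conclusion.** The departure from Protocol 11.5.3 is real, disclosed and justified only by brevity. Its effect is that the antibody part of the IIV4 priming question is summarized only in PP, and that SAP 6.1 and section 12 do not fit together.

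Two wider readings fail. The whole priming question has not lost its mITT analysis: Tables 24 and 25 follow the Table 22 format, which repeats for Days 186 and 200, so T cell responses to M-001 peptides after IIV4 remain in mITT (without p-values). Responses to seasonal and pandemic antigens (Tables 26 to 29) are PP only. Nor do the documents show that the Day 200 estimates will move by any given amount. They give no seroconversion rate and no Day 200 exclusion rate, and the shifts of about 2.5, 5 and 7 to 8 points are extreme bounds that require every excluded subject to have titers and to respond alike.

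This is a modest point, worth acting on because the repair is cheap.

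**What to change.** Add mITT versions of SAP Tables 30 to 37, labeled as a sensitivity analysis. At a minimum cover seroconversion from Day 172 to Day 200, and titer of at least 40 and GMT at Days 172 and 200. State the number contributing in each arm, since mITT will not recover everyone. Use Day 172 as the baseline for that seroconversion, as SAP 3.2.2 does; SAP 3.3 sets the pre-vaccination value for fold rise at Day 1, and the two should be reconciled. If the sponsor prefers not to restore the tables, section 12 should give a scientific reason.

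Reconcile SAP 6.1 with section 12, so that the intercurrent-infection comparison refers to analyses that exist. Settle whether baseline ineligibility excludes a subject from mITT (SAP 6.3.1 against the Table 14 shell).

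The cost is re-running existing table code on a second population and up to eight more tables in the report. No new data or assays are needed.

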9.1 Overall Study Design and Plan Description

Table 1: Study Design

Study Arm	Dose 1 Day 1	Dose 2 Day 22	Dose 3 Day 172
A (n=60)	1 mg M-001	1 mg M-001	IIV4
B (n=60)	Placebo	Placebo	IIV4

9.5.1 Efficacy/Immunogenicity and Safety Measurements Assessed and Flow Chart

Table 2: Schedule of Study Procedures

Study Visit (V)	01	02	03	04	05	06	07	08	09	10	11	12
Study Day	1	9	15	22	30	36	43	78	172	186	200	200 ⁺
Visit Windows		(+2)	(+2)	(+2)	(+2)	(+2)	(+7)	(+7)	142-202	(+3)	(+7)	(+14)
Sign Consent Form ¹	X											
Assess eligibility	X			X					X			
Collect demographic information	X											
Review Medical History	X		X	X		X	X	X	X	X	X	X
Concomitant meds	X	X	X	X	X	X	X	X^7	X^7	X^7	X ⁷	X^7
Vital signs ²	X	{X}	{X}	X	{X}	{X}	{X}	{X}	X	{X}	{X}	
Height, Weight	X											
Targeted Physical Exam	{X}	{X}	{X}	{X}	{X}	{X}	{X}	{X}	{X}	{X}	{X}	
Review contraception/ Counseling ³	X	X	X	X	X	X	X	X	X	X		
Pregnancy Test ^{2,4}	X			X					X			
Blood - Safety Labs (10 mL)	X	X			X							
Blood – Antibody Assays (10-20 mL)	X			X			X	X	X*		X*	
Blood – PBMCs (40-60 mL)	X=		X			X	X=	X	X	X	X	
Randomization	X											
AE/SAE Assessment ^{2#}	X	X	X	X	X	X	X	X	X	X	X	X
Vaccination ⁴	X ⁵			X ⁵					X			
Evaluate vaccination site	X	X		X	X							
Postvaccination procedures ⁶	X			X								
Review Memory Aid Data		X			X							
Blood volume (mL)	80	10	40	10	10	40	70	50	60	40	60	
required at this visit only if clinically indica	atad						•					

^{ } required at this visit only if clinically indicated

Consent process completed and form signed before any study-related procedures are conducted.

Vital signs include blood pressure, pulse, and oral temperature. On vaccination visits, these items should be completed prior to vaccination.

Counseling on avoidance of pregnancy for women of childbearing potential.

Urine or serum pregnancy test must be negative and be completed within 24 hours prior to vaccination for women of childbearing potential.

All subjects will be observed for a minimum of 20 minutes following vaccination.

⁶Post-vaccination procedures will include documentation of any reactogenicity during the observation period and any AEs/SAEs post-vaccination, as well as provision of Memory Aid and instructions on completion.

⁷ Concomitant medications (vaccines only) will be recorded on the appropriate data collection form after Visit 7 through the end of the study.

*Visit 12 will occur as a phone call only if visit 11 occurs prior to Study Day 200.

*20 mL of blood will be collected for antibody assays on these days; 10 mL will be collected on other days of collection for antibody assays

60 mL of blood will be collected for PBMCs on these days; 40 mL will be collected on other days of PBMC collection

*AEs will be limited to SAEs after 21 days after M-001 study vaccinations.

9.7.1 Sample Size

Table 3: Power (%) to Detect Safety Events

Event Frequency	Single Study Arm N=60	Two Study Arms N=120
≥10% Very Common	99.8	>99.9
≥1% Common	45.3	70.1
≥0.1% Uncommon	5.8	11.3
≥0.01% Rare	<1	1.2

Table 4: Precision of Binomial Confidence Intervals

	N	95% CI
Single Study Arm	60	(36.8, 63.2)
Two Study Arms	120	(40.7, 59.3)

Table 5: Power Analysis for Primary Immunogenicity Endpoint

GMP _e /GMT _c {fold-change}	$\begin{array}{c} log_{10}\left(GMP_{M}\right) - log_{10}\left(GMP_{c}\right) \\ \{log\text{-}difference}\} \end{array}$	Std Dev log ₁₀ (GMP)	Power (N = 60)	Power (N=54) 10% drop out
		0.25	97	96
1.5	0.18	0.50	49	45
		0.75	26	23
		0.25	>99	>99
2	0.30	0.50	90	87
		0.75	58	54
		0.25	>99	>99
3	0.48	0.50	>99	99
		0.75	93	90
		0.25	>99	>99
4	0.60	0.50	>99	>99
		0.75	99	98

10.2 Protocol Deviations

Table 6: Distribution of Protocol Deviations by Category, Type, and Study Arm (All Enrolled Subjects)

[Implementation Note: Include all deviation types collected in the study, even if not listed here; do not include categories with zero deviations reported for All Subjects.]

	Deviation Type	Group A: 1 mg M- 001 (N=X)		Group B: Placebo (N=X)		All Subjects (N=X)	
Category		No. of Subj.	No. of Dev.	No. of Subj.	No. of Dev.	No. of Subj.	No. of Dev.
Eligibility/enrollment	Any type						
	Did not meet inclusion criterion	Х	х	Х	Х	х	Х
	Met exclusion criterion						
	ICF not signed prior to study procedures						
	Other						
Treatment administration schedule	Any type						
	Out of window visit						
	Missed visit/visit not conducted						
	Missed treatment administration						
	Delayed treatment administration						
	Other						
Follow-up visit schedule	Any type						
	Out of window visit						
	Missed visit/visit not conducted						
	Other						
Protocol procedure/assessment	Any type						
	Incorrect version of ICF signed						
	Blood not collected						
	Too few aliquots obtained						
	Specimen result not obtained						
	Required procedure not conducted						
	Required procedure done incorrectly	_					
	Study product temperature excursion						
	Specimen temperature excursion						
	Other						

		0	a: 1 mg M- 001 (=X)	Group B: Placebo (N=X)		All Subjects (N=X)	
Category	Deviation Type	No. of Subj.	No. of Dev.	No. of Subj.	No. of Dev.	No. of Subj.	No. of Dev.
Treatment administration	Any type						
	Required procedure done incorrectly						
	Study product temperature excursion						
	Other						
Blinding policy/procedure	Any type						
	Treatment unblinded						
	Other						
Note: N=Number of subjects	enrolled	1	ı		I	I	l

12.2.2 Displays of Adverse Events

Table 7: Subjective Systemic Reactogenicity Grading

Mild (Grade 1)	Moderate (Grade 2)	Severe (Grade 3)
No interference with daily activity	Some interference with daily activity	Significant interference, prevents daily activity
No interference with daily activity	Some interference with daily activity	Significant interference, prevents daily activity
No interference with daily activity	Some interference with daily activity	Significant interference, prevents daily activity
No interference with daily activity	Some interference with daily activity	Significant interference, prevents daily activity
No interference with daily activity	Some interference with daily activity	Significant interference, prevents daily activity
No interference with daily activity	Some interference with daily activity	Significant interference, prevents daily activity
No interference with daily activity	Some interference with daily activity	Significant interference, prevents daily activity
	No interference with daily activity No interference with	daily activity No interference with daily activity Some interference with daily activity Some interference with daily activity Some interference with daily activity No interference with Some interference with daily

Table 8: Quantitative Systemic Reactogenicity Grading

Systemic (Quantitative)	Mild (Grade 1)	Moderate (Grade 2)	Severe (Grade 3)
Fever* - oral [†]	38.0°C – 38.4°C	38.5°C – 38.9°C	>38.9°C
	100.4°F – 101.1°F	101.2°F – 102.0°F	>102.0°F

Note: Oral temperature assessed on Day 1 prior to the first primary series study vaccination will be considered as baseline.

^{*} A fever can be considered not related to the study product if an alternative etiology can be documented.

[†] Subjects must not eat or drink anything hot or cold, or smoke within 10 minutes prior to taking oral temperature.

Table 9: Injection Site Reactogenicity Grading

Injection Site Reaction	Mild (Grade 1)	Moderate (Grade 2)	Severe (Grade 3)
Pain – experienced without touching the injection site (spontaneous discomfort)	Subject is aware of pain, but it does not interfere with daily activity, and no pain medication is taken	Subject is aware of pain; there is interference with daily activity or it requires repeated use of a non-narcotic pain reliever for >24 hours	Subject is aware of pain, and it prevents daily activity or requires any use of a narcotic pain reliever
Tenderness – hurts only when injection site is touched or the arm is moved	The area immediately surrounding the injection site hurts only when touched or with arm motion, and it does not interfere with daily activity	The area immediately surrounding the injection site hurts when touched or with arm motion, and it interferes with daily activity	The area immediately surrounding the injection site hurts when touched or with arm motion, and it prevents daily activity
Pruritus	Does not interfere with daily activity	Interferes with daily activity	Prevents daily activity
Ecchymosis*	Does not interfere with daily activity	Interferes with daily activity	Prevents daily activity
Erythema*	Does not interfere with daily activity	Interferes with daily activity	Prevents daily activity
Induration/Edema*	Does not interfere with daily activity	Interferes with daily activity	Prevents daily activity
*Will be also measured in mm b	out size will not be used as halting crite	eria.	

Table 10: Injection Site Reactogenicity Measurements

Injection Site Reaction	Small	Medium	Large			
Ecchymosis *	<20 mm	20 mm – 50 mm	>50 mm			
Erythema*	<20 mm	20 mm – 50 mm	>50 mm			
Induration /Edema*	<20 mm	20 mm – 50 mm	>50 mm			
* Will not be used as halting criteria.						

Table 11: Pulse and Blood Pressure Grading

Physiologic Parameter	Mild (Grade 1)	Moderate (Grade 2)	Severe (Grade 3)
Bradycardia - beats per minute	45 – 49	40 – 44	<40
Tachycardia - beats per minute	116 – 130	131 – 155	>155
Hypotension (systolic) mm Hg	80 – 84	75 – 79	<75

